Summary:	This study is an open-label, baseline-controlled, single-center study to measure the change in skin elasticity after combined radio frequency (RF) and pulsed electromagnetic field (PEMF) treatment. Forty-five adult females will undergo weekly treatments over a period of 8 weeks. Skin elasticity will be measured by a Cutometer® prior to beginning treatment, week 7 and 3 months after completion of treatment. Photographs will be taken prior to treatment, at week 4, week 7 and 3 months after completion of treatment. Patient discomfort/pain and satisfaction questionnaires will be completed before, during and after treatment.
Objectives:	The objective is to determine the quantitative change in elasticity of facial skin in subjects who have undergone treatment with combined RF and PEMF.
Endpoint	
Primary endpoint:
 
Quantitatively and objectively measure the change in facial skin elasticity following combined radio frequency and electromagnetic treatment. 
Secondary endpoints:
 
Improvement in facial skin laxity at 7 and 20 weeks post-intervention compared to baseline as assessed by blinded evaluators by photographic assessment utilizing the Fitzpatrick Wrinkle and Elastosis Scale (FWES) scale.Improvement in subject appearance at 7 and 20 weeks post-intervention compared to baseline as assessed by the subject utilizing the Global Aesthetic Improvement Scale (GAIS)Improvement in subject satisfaction with facial skin laxity at 4, 7 and 20 weeks post-intervention compared to baseline as measured by the 5-point Likert Subject Satisfaction questionnaire.
Population:	The study will enroll approximately 45 healthy adult females desiring improvement in facial skin elasticity and tightness.
Phase:	Post-approval
Number of Sites enrolling participants:	One site
Description of Study Agent:	Venus Versa is an FDA approved aesthetic device. The Diamondpolar applicator combining multi-polar RF and PEMF energies will be used in this study. It is approved for non-invasive skin tightening of the face in skin types I - IV.
Study Duration:	8 months

Participant Duration: 5 months

SCHEMATIC OF STUDY DESIGN

2 INTRODUCTION: BACKGROUND INFORMATION AND SCIENTIFIC RATIONALE

2.1 BACKGROUND INFORMATION

The Venus Versa is a multi-application device used in aesthetic and cosmetic procedures, approved by the FDA for over 20 indications. It is comprised of a console and ten detachable applicators. The system can deliver three types of energies using the associated applicators - radiofrequency (RF), pulsed electromagnetic field (PEMF) and intense pulse light (IPL). The Diamondpolar applicator used in this study [combining multi-polar radiofrequency (RF) and pulsed electromagnetic field (PEMF) energies] is approved for non-invasive skin tightening of the face in Fitzpatrick skin types I - IV.

The Cutometer® is a non-invasive measurement device that measures the viscoelastic properties of human skin using the suction method. Negative pressure is created in the device and the skin is drawn into the aperture of the probe. Inside the probe, the penetration depth is determined by a non-contact optical measuring system. This optical measuring system consists of a light source and a light receptor, as well as two prisms facing each other, which project the light from transmitter to receptor. The light intensity varies due to the penetration depth of the skin. The resistance of the skin to be suctioned by the negative pressure (firmness) and its ability to return into its original position (elasticity) are displayed as curves at the end of each measurement.

Ryu et al determined that skin aging of women could be expressed numerically by measuring the skin elasticity using a Cutometer®.¹ A distinct trend in aesthetic medicine is the patient's demand for

efficient, noninvasive treatments with no downtime. These treatments are expected to be as safe and painless as possible. A technique based on a combination of RF and PEMF has shown to be effective in the treatment of facial wrinkles and is virtually pain free.² These previous studies focused on the photographic appearance of the skin pre- and post-treatment as judged by blinded raters. To date, there are no studies which use objective parameters to determine treatment efficacy. This study will determine if the Cutometer® can provide objective evidence of treatment efficacy.

2.2 RATIONALE

The combination RF and PEMF technology has already been proven to be safe and effective in the improvement of skin laxity. However, to date, there is no study that quantitatively analyzes the degree of improvement.

The objective of this clinical study is to evaluate the use of the Cutometer® in providing objective evidence of improvement in facial skin elasticity after treatment with combined RF and PEMF technology in adult females seeking treatment for the aesthetic appearance of facial wrinkles.

2.3 POTENTIAL RISKS AND BENEFITS

2.3.1 KNOWN POTENTIAL RISKS

The potential risks for adverse effects of the treatment procedure include but are not limited to temporary swelling, redness, pain and burns at treatment site. The following long range risks were also identified as low probability adverse events: scarring, skin breakdown and hyper or hypopigmentation.

Previous studies have shown the immediate risks outlined above are transient and generally well-tolerated by patients. The long-range risks outlined above are theoretical, as there have been no reports of these incidences.

2.3.2 KNOWN POTENTIAL BENEFITS

If the subject agrees to be in this study, she will be contributing to the understanding of the Cutometer®'s ability to quantify the device's impact on the degree of skin rejuvenation, skin tightening and improved appearance of facial rhytids. In addition, the subject may benefit from improvement in skin laxity in the treated areas.

3 OBJECTIVES AND PURPOSE

Primary objective:

Quantitatively and objectively measure the change in facial skin elasticity following combined radio frequency and electromagnetic treatment.

Secondary objectives:

Improvement in skin laxity at 20 weeks post-intervention compared to baseline as assessed by blinded evaluators by photographic assessment utilizing the Fitzpatrick Wrinkle and Elastosis Scale (FWES) scale.

Improvement in subject appearance at 7 and 20 weeks post-intervention compared to baseline as assessed by the subject utilizing the Global Aesthetic Improvement Scale (GAIS).

Improvement in subject satisfaction with skin laxity at 4, 7 and 20 weeks post-intervention compared to baseline as measured by the 5-point Likert Subject Satisfaction questionnaire.

4 STUDY DESIGN AND ENDPOINTS

4.1 DESCRIPTION OF THE STUDY DESIGN

This is an open-label, baseline-controlled, single-center study to objectively measure the change in skin elasticity after combined radio frequency and electromagnetic treatment

4.2.1 PRIMARY ENDPOINT

As skin ages, collagen can become disorganized, causing changes in both the mechanical property of the skin and skin appearance. The change in gross elasticity ($R2$ or Ua/Uf which is a ratio of maximum recovery (Ua) and skin distensibility (Uf)) as measured by a Cutometer® has been found to be one of the most suitable parameters to represent the influence of aging on skin mechanical properties.¹ This is expressed as a percentage, the closer the value is to 1 (100%), the more elastic the skin. Thus, the primary endpoint will be the change in gross elasticity after treatment with combined RF and PEMF. The gross elasticity of facial skin will be measured prior to the start of the treatment regimen (baseline), and 20 weeks after completion of the treatment regimen.

4.2.2 SECONDARY ENDPOINTS

Secondary endpoint #1: Change in photographic appearance of rhytids, as determined by blinded Facial Plastic & Reconstructive surgeons using the Fitzpatrick Wrinkle and Elastosis Scale (FWES) from baseline to week 20. Photographs from weeks 4 and 7 will only be used to track treatment progress, and will not be used by the raters to determine treatment efficacy.

Secondary endpoint #2: To assess clinical efficacy subjectively, the subjects will complete the Global Aesthetic Improvement Scale (GAIS), which is a 7-grade instrument.

Secondary endpoint #3: To assess satisfaction with the treatment, subjects will complete a 5-point Likert Subject Satisfaction scale.

The secondary endpoints serve to augment the findings of the primary endpoint. They help to provide a more complete understanding of treatment efficacy by including evaluations by trained physicians as well as the subjects themselves.

4.2.3 EXPLORATORY ENDPOINTS

None

5 STUDY ENROLLMENT AND WITHDRAWAL

5.1 PARTICIPANT INCLUSION CRITERIA

In order to be eligible to participate in this study, an individual must meet all of the following criteria:

1. Healthy adult female subject at least 18 years of age and older with Fitzpatrick skin types I-IV who are willing to participate.
2. Women requesting treatment for skin laxity of the face.
3. Able to read, understand and voluntarily provide written Informed Consent.
4. Able and willing to comply with the treatment/follow-up schedule and requirements.
5. Ability to tolerate the RF/PEMF procedure, and willing to adhere to the treatment regimen.

5.2 PARTICIPANT EXCLUSION CRITERIA

An individual who meets any of the following criteria will be excluded from participation in this study:

1. Having any active electrical implant anywhere in the body, such as a pacemaker or an internal defibrillator.
2. Having a permanent implant in the treated area.
3. Prior use of retinoids in treated area within 2 weeks of initial treatment or during the course of the study.
4. Use of oral Isotretinoin (Accutane®) within 6 months of initial treatment or during the course of the study.
5. Patient on systemic corticosteroid therapy 6 months prior to and during the course of the study.
6. Prior use of collagen, fat injections and /or other methods of skin augmentation (enhancement with injected or implanted material) in treated area within 4-6 weeks of initial treatment or during the course of the study. Treatment may not be performed at all over permanent dermal implants.
7. Prior ablative resurfacing procedure in treated area with laser or other devices within 12 months of initial treatment or during the course of the study.
8. Any other surgery in treated area within 12 months of initial treatment or during the course of the study.
9. History of keloid formation or poor wound healing in a previously injured skin area.
10. History of epidermal or dermal disorders (particularly if involving collagen or micro vascularity).
11. Open laceration or abrasion of any sort on the area to be treated.
12. History of immunosuppression/immune deficiency disorders (including HIV infection or AIDS) or use of immunosuppressive medications.

13. Having any form of active cancer at the time of enrollment and during the course of the study.
14. Significant concurrent illness, such as uncontrolled diabetes i.e. any disease state that in the opinion of the Investigator would interfere with the treatment, or healing process.
15. Participation in a study of another device or drug within 1 month prior to study enrollment or during this study, and as per the Investigator's careful discretion, as long as not contradictory to any of the above criteria.
16. Tattoos in the treatment area.
17. Mentally incompetent, prisoner or evidence of active substance or alcohol abuse.

5.3 STRATEGIES FOR RECRUITMENT AND RETENTION

Approximately 45 subjects will be recruited through the site investigator's outpatient clinic. Potential subjects will be identified through the existing database of over 20,000 patients and a recruitment email with a brief description of the study will be sent. In addition, an ethics-approved flyer will be posted in the patient waiting area of the clinic. It is also anticipated that a substantial number of participants will be recruited through word of mouth.

To enhance participant retention, email and phone calls will be employed to remind patients of treatment and follow up appointments.

No financial incentives will be offered, however the potential for improved aesthetic appearance is a compelling non-financial incentive.

5.4 PARTICIPANT WITHDRAWAL OR TERMINATION

5.4.1 REASONS FOR WITHDRAWAL OR TERMINATION

Subjects are free to withdraw from participation in the study without prejudice at any time upon request. In the event that a subject drops out of the study or is withdrawn from the study, the Exit/Termination CRF form should be completed. On the withdrawal page, the Investigator should record the date of the withdrawal, the person who initiated withdrawal and the reason for withdrawal.

Reasonable effort will be made to contact any subject lost to follow up during the course of the study in order to complete assessments and retrieve any outstanding data and study medication/supplies. The records of subjects who terminate prior to completing the study will be retained and the reason for termination will be documented.

An investigator may terminate participation in the study if:

- Any clinical adverse event (AE), laboratory abnormality, or other medical condition or situation occurs such that continued participation in the study would not be in the best interest of the participant.
- The subject meets an exclusion criterion (either newly developed or not previously recognized) that precludes further study participation.

5.4.2 HANDLING OF PARTICIPANT WITHDRAWALS OR TERMINATION

Every effort will be made to continue follow-up of withdrawn or terminated subjects or subjects who discontinue the intervention but remain in the study for follow-up, especially for safety and efficacy study endpoints. Every effort will be made to undertake protocol-specified safety follow-up procedures to capture AEs, serious adverse events (SAEs), and unanticipated problems (UPs). Subjects that withdraw will be replaced until a maximum of 60 subjects are randomized with 45 subjects expected to complete the study. Subjects that withdraw or are terminated from the study will still be requested to complete the week 20 follow-up procedure in order to evaluate for possible AEs or unanticipated problems (UPs).

5.5 PREMATURE TERMINATION OR SUSPENSION OF STUDY

This study may be temporarily suspended or prematurely terminated if there is sufficient reasonable cause. Written notification, documenting the reason for study suspension or termination, will be provided by the suspending or terminating party to the principal investigator (PI) and Venus Concept. If the study is prematurely terminated or suspended, the PI will promptly inform the ethics board and will provide the reason(s) for the termination or suspension.

Circumstances that may warrant termination or suspension include, but are not limited to:

- Determination of unexpected, significant, or unacceptable risk to participants
- Demonstration of efficacy that would warrant stopping
- Insufficient compliance to protocol requirements
- Data that are not sufficiently complete and/or evaluable
- Determination of futility

Study may resume once concerns about safety, protocol compliance, data quality are addressed and satisfy the sponsor, ethics board and/or regulatory authorities.

6 STUDY AGENT

6.1 STUDY AGENT(S) AND CONTROL DESCRIPTION

6.1.1 ACQUISITION

The investigational device will be shipped to the investigative site directly from the sponsor. An activation code will be required to activate the device. This code will not be provided to the investigative site until all regulatory and institutional review board (IRB) approvals are in place and the site has received training for both the device and the study.

6.1.2 DEVICE SPECIFIC CONSIDERATIONS

The Venus Versa (MP)² by Venus Concept Ltd. is a non-invasive dermatological treatment system based on patented and proprietary (MP)² technology which combines Multi Polar Radiofrequency (RF) and Pulsed Magnetic Fields. The RF energy penetrates the skin and results in RF-generated tissue heating that has known effect on skin laxity. The magnetic field that is simultaneously induced increases fibroblast collagen production through a non-thermal mechanism and contributes to the clinical effect

of skin laxity improvement. The Diamondpolar applicator used for this study includes electrodes that deliver the Multi Polar Radiofrequency (RF) and Pulsed Magnetic Fields energy.

6.2 STUDY AGENT ACCOUNTABILITY PROCEDURES

The device will be shipped to the site by the sponsor. The device will require an activation code in order to function. The activation code will only be provided once all the ethics and regulatory approvals for the site are in place. The treatments will be administered by a trained technician according to the protocol under direct supervision of the PI. When not in use, the device will be turned off and kept in a locked room. At the end of the study, the device will be returned to the sponsor.

7 STUDY PROCEDURES AND SCHEDULE

7.1 STUDY PROCEDURES/EVALUATIONS

7.1.1 STUDY SPECIFIC PROCEDURES

- Medical history: obtained through interview. History will include age, other medical conditions, and previous invasive or non-invasive cosmetic procedure to the face or neck in the last 6 months.
- Medication history: current medications will be obtained through interview and will include prescription, over the counter, and herbal medications taken 4 weeks prior to study enrollment.
- Physical examination: completed by PI. Focused head and neck skin assessment that will include Fitzpatrick skin type and evidence of scars, infection, or inflammation of the face or neck.
- Imaging assessment: standard photos of the treated area will be taken by the PI using a Nikon D3100 using a 105 mm lens with fixed 2 Nikon flashes using diffuse bounce flash technique that reduces shadows and accentuates the subject's contours.
- Cutometer assessment at baseline, week 7 and at week 20.
- Rater assessment: The FWES will be used to rate the level of skin aging.
- Patient-reported outcomes: subjects will be asked to complete the GAIS questionnaire at weeks 7 and 20, and a 5-point Likert subject satisfaction scale at weeks 4, 7 and 20.

7.2 LABORATORY PROCEDURES/EVALUATIONS

7.2.1 CLINICAL LABORATORY EVALUATIONS

Not applicable

7.2.2 OTHER ASSAYS OR PROCEDURES

Not applicable

7.3 STUDY SCHEDULE

7.3.1 SCREENING

If the subject meets the preliminary study criteria the study doctor, and/or his/her designee, will obtain an informed consent from the subject, clearly indicating her understanding of the requirements and possible risks involved with study participation and other applicable treatment options.

During the first visit, the study investigator, and/or his/her designee, will screen the subject for eligibility to participate in the clinical study using the inclusion/exclusion criteria. During screening the study doctor will review the subject's medical/surgical history, and examine the subject's targeted area to ensure that it meets the study criteria. The subject will complete screening and the treatment will be scheduled.

Enrollment/baseline visit can be conducted on the same day as screening or up to 30 days after screening.

7.3.2 ENROLLMENT/BASELINE

Enrollment/Baseline Visit (Visit 1, Week 0)

Once a subject has been confirmed that they continue to meet inclusion/exclusion criteria, each subject will receive a unique identifying number that will be composed of a two-digit site number and a three-digit subject number in sequence. This unique identifier will be used throughout the entire study and will be entered in the subject's CRF for each treatment.

Baseline Cutometer® measurements of the area to be treated will be obtained.

Subjects will be asked to refrain from using skin products or medications containing ingredients listed in the exclusion criteria, and may have to undergo washout periods for any such substances or medications prior to receiving treatment as part of this study. The Investigator should review the subject's skin care regimen and suggest appropriate alternatives for the course of the study, as needed.

All subjects will have photographs taken of the area to be treated. All subjects will be asked to remove all jewelry and piercings and wash the area to be photographed with provided cleanser to remove all makeup and skincare products. Subject will then wait 10 minutes for any washing related erythema to subside prior to initiation of photography session. All stray hairs will then be pulled away from the face. If seated photos, the stool height will be adjusted to ensure the subject's head, neck and spine are aligned and the subject is sitting up straight. Subject will then be positioned so they are centered in the frame using chin and forehead rests as applicable for seated three-point photo capture and if standing, feet are aligned with standardized photo foot marking on the floor standing straight with back flat against the draped back drop (blue, green or white) wall. All photography is to take place within the same room with standardized lighting, no natural light, for the duration of the study.

Standardized photographs will be taken using a high quality digital SLR camera to obtain three photos (frontal 90°, right 45° and left 45°). These photographs will be used as an assessment tool. They may also be used for publication and/or presentation of the study findings and generalized characterization of the disease state. Moreover, they may use the photographs for marketing or other commercial purposes.

The photos will be taken in a private room or area. The investigative site will ensure that digital photography equipment with standardized illumination and background is available for use during this study. Digital photos will be stored on dedicated media. A copy of all study photographs will be transferred to Venus Concept at the end the study or as part of interim analysis. Only the subject code will appear on the records being transferred to the sponsor to ensure anonymity of the subjects.

Study visits that include photography: Baseline, week 4, week 7, week 20.

Standard conditions: The photos should be taken in standardized conditions, including distance, angle, background, and illumination in order to achieve high-quality before & after sets. Do not use direct illumination.

Subject posture: The subject will be placed in the same position each time. As each photograph is taken, it should be viewed to ensure that it is in focus and is similar to its baseline counterpart in all technical aspects, including lighting, distance and angle.

Order of photos: the first photograph in each session should be of an identification card that will include subject code and visit details.

File names: The digital files should follow a consistent standard naming scheme, for example: 01-001TS_Tx1_face.

Treatment Procedure (also see user manual)

During each treatment session, subjects will be treated with the Venus Versa system using the Diamondpolar applicator as per standard treatment parameters.

Prior to the treatment, glycerin in gel formulation should be applied thoroughly to the treatment area.

In the initial treatment it is important to adjust the treatment required energy level to best suit the patient's tolerance to the treatment. Tolerance will increase as the patient becomes more familiar with the treatments.

The aim of the procedure is to heat the surface of the skin on the treatment area and raise the temperature up to at least 39°C and maintain it for a minimum of 5 minutes. Always aim for the highest temperature that the subject can tolerate. The treatment should be monitored with an external infrared (IR) thermometer.

During the procedure, the applicator's electrodes will press against the patient's skin, making sure that all electrodes are in contact with the skin as much as possible.

The applicator strokes are long and continuous, and performed in form of "8" figures, circles, ellipses or waves. The applicator will always be in motion, while in contact with the skin surface.

If the measured skin surface temperature (as measured by the IR thermometer) is less than 39°C, treatment is not optimal and the desired results will not be accomplished. The achieved skin temperature depends on the applicator movement speed and energy level. The lower the energy, the slower the movement will be and vice-versa.

In the event that the patient experiences discomfort or pain during the treatment, either the energy percentage will be decreased, more glycerin in gel should be applied or wider and quicker movements should be performed. Treatment may also be halted.

Subject discomfort evaluation

The subject will record their assessment of discomfort/pain on a 100 mm VAS CRF page immediately after each treatment which will be considered to be a source document.

Skin safety – immediate response after procedure

Local (dermal) tolerability examination (only on the face) will be performed immediately following treatment at the time-points given in the Study Visit Table and will include assessments of pain during treatment, hemorrhage, burn, erythema, edema or other reactions. All tolerability assessments must be completed by the same person throughout the study whenever possible. Local tolerability on the face will be rated as none, mild, moderate, or severe.

Subjects should remain in the research setting at least 30 minutes after treatment in order to ensure their well-being.

Subjects will be discharged from the clinic and will be instructed to return for the Visit 2, Week 1 assessment and treatment.

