Subjects will be discharged from the clinic and will be instructed to return for the Visit 6, Week 5 assessment and treatment.

Visit 6, Week 5

Subjects will return to the clinic one week (± 3 days) after the last treatment. Adverse events and any changes to concomitant medications will be recorded.

Subjects will receive treatment of the face as described above in section 7.3.2. Following treatment, the investigator will examine the treated area and report immediate response.

The assessment of discomfort/pain will be based on the subject's completion of the 100 mm VAS immediately after treatment.

Subjects will be discharged from the clinic and will be instructed to return for the Visit 7, Week 6 assessment and treatment.

Visit 7, Week 6

Subjects will return to the clinic one week (± 3 days) after the last treatment. Adverse events and any changes to concomitant medications will be recorded.

Subjects will receive treatment of the face as described above in section 7.3.2. Following treatment, the investigator will examine the treated area and report immediate response.

The assessment of discomfort/pain will be based on the subject's completion of the 100 mm VAS immediately after treatment.

Subjects will be discharged from the clinic and will be instructed to return for the Visit 8, Week 7 assessment and treatment.

Visit 8, Week 7

Subjects will return to the clinic one week (± 3 days) after the last treatment. Adverse events and any changes to concomitant medications will be recorded. Photographs will be taken as described above in section 7.3.2. Cutometer® measurements of the treated area will be obtained.

Subjects will receive treatment of the face as described above in section 7.3.2. Following treatment, the investigator will examine the treated area and report immediate response.

The assessment of discomfort/pain will be based on the subject's completion of the 100 mm VAS immediately after treatment.

Subjects will complete the GAIS scale and the 5-point Likert satisfaction scale.

Subjects will be discharged from the clinic and will be instructed to return for the final study visit, Visit 9, Week 20 assessment.

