7.3.4 FINAL STUDY VISIT

Visit 9, Week 20

Subjects will return to the clinic twelve weeks (± 2 weeks) after the last treatment for the final visit. Adverse events and any changes to concomitant medications will be recorded. Photographs will be taken as described above in section 7.3.2. The subject will complete the GAIS scale and the 5-point Likert satisfaction scale. Cutometer® measurements of the treated area will be taken.

The termination form will be completed and subjects will be discharged from the clinic and terminated from the study. The PI will record all reportable events with start dates occurring any time after informed consent is obtained until 7 (for non-serious AEs) or 30 days (for SAEs) after the last day of study participation.

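### Late skin effects, named as long-range risks, rest on general adverse-event inquiry and unread photographs: no treated-area examination is scheduled at Visit 9, and no contact in the 10-14 weeks after the last treatment

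*Combined protocol and SAP*

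**What the plan says.** **Named risks.** Section 2.3.1 lists swelling, redness, pain and burns as possible effects of treatment, then adds a second group: "The following long range risks were also identified as low probability adverse events: scarring, skin breakdown and hyper or hypopigmentation". It calls these theoretical: "The long-range risks outlined above are theoretical, as there have been no reports of these incidences". Section 8.2.3 counts scarring, hyper- and hypopigmentation, blistering, crusting and hair loss among the expected AEs.

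**Structured skin check.** Section 7.3.2 (Skin safety) states: "Local (dermal) tolerability examination (only on the face) will be performed immediately following treatment at the time-points given in the Study Visit Table". The check "will include assessments of pain during treatment, hemorrhage, burn, erythema, edema or other reactions", each rated none, mild, moderate or severe. The visit text in 7.3.3 keeps the same order, for example: "Following treatment, the investigator will examine the treated area and report immediate response".

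**Schedule.** In 7.3.7 the immediate-response row is marked at Visits 1-8 and the physical-exam row at screening only. Under 7.1.1 that physical examination is the one that looks for scars, infection and inflammation of the face and neck.

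**Last treatment to final visit.** Section 7.3.4: "Subjects will return to the clinic twelve weeks (± 2 weeks) after the last treatment for the final visit". Visit 9 then consists of AE and medication recording, photographs, the GAIS and satisfaction scales, and Cutometer readings. Under 5.4.2, women who withdraw are asked to "complete the week 20 follow-up procedure in order to evaluate for possible AEs or unanticipated problems (UPs".

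**The concern.** The plan separates immediate from long-range skin effects, yet its only structured skin check after baseline is aimed at the first group. The examination that looks for scars is done before treatment and never repeated. The visit to which withdrawn women are recalled for AE evaluation contains no examination of the treated skin.

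What is at stake is how a clean result can be read. If the report states that no scarring or pigment change was seen, its weight depends on how completely late changes would have been found. With a general question and photographs taken for another purpose, that completeness is unknown. Contact is also uneven: an AE inquiry follows each of the first seven treatments within days, but follows the eighth only after months. An effect of the last session that came and went in between would depend on the woman making contact or remembering it.

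**Working it through.** **Step 1. Contact intervals** (inputs: 7.3.3 and 7.3.4)
- After treatments 1-7, the next visit is at 7 ± 3 days: 7 - 3 = 4 to 7 + 3 = 10 days.
- After treatment 8, the next visit is at 12 ± 2 weeks: 10 to 14 weeks, or 10 × 7 = 70 to 14 × 7 = 98 days.
- Counted from Week 7, Visit 9 falls in study weeks 17 to 21. The Week 20 label (20 - 7 = 13 weeks after the last treatment) lies inside that window.

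**Step 2. What is scheduled** (inputs: 7.3.7 checked against 7.3.2-7.3.4)

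| Item | Visits 1-8 | Visit 9 |
|---|---|---|
| Treated-area examination | 8, each after that day's treatment | 0 |
| Physical examination including scars | screening only | 0 |
| AE recording | every visit | 1 |
| Photographs | baseline, weeks 4 and 7 | 1 |

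The visit text agrees with the table on each row.

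**Step 3. Who reads the photographs for safety** (inputs: 4.2.2, 7.3.2, 10.6.1)
- Photographs from weeks 4 and 7 serve only to track treatment progress.
- Week-20 photographs go to raters who score wrinkles and elastosis. These raters are blinded to treatment stage, so they are poorly placed to call a mark new.
- The instruction to view each photograph as it is taken concerns focus and technical match to baseline.
- No section asks anyone to record scars or pigment change from them.

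**Step 4. What zero events would show** (input: 45 women expected to complete, 5.4.2)
- With full detection, the one-sided 95% upper limit for 0 of n is 1 - 0.05^(1/n). For n = 45 this is 1 - 0.05^(1/45) = 0.0644, or 6.4%.
- If only a fraction d of events is detected, the limit on the true rate is 0.0644 / d. The documents give no value for d, so the following values are assumptions:
  - d = 0.90: 0.0644 / 0.90 = 7.2%
  - d = 0.75: 0.0644 / 0.75 = 8.6%
  - d = 0.50: 0.0644 / 0.50 = 12.9%

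The plan states no figure of its own for late effects, so there is none to reproduce beyond the visit window in Step 1.

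**The case against.** A reader might infer that late effects are never looked for, or that no woman is examined when they could appear. The documents do not support either reading.
- The investigator asks about AEs at every visit (8.3). AEs are recorded at Visit 9, and scarring and pigment change are on the expected list (8.2.3).
- At week 20 the investigator photographs the washed face in three views under standard conditions (7.1.1, 7.3.2), and the Cutometer probe is applied to the treated skin. A persisting visible lesion may well be noticed, whether or not the woman mentions it.
- The examinations at Visits 2-8 come 4-10 days after the preceding session and include an open item for other reactions, so lasting changes from earlier sessions could be recorded there. The documents give no onset time for the long-range risks, so it cannot be said that every examination comes too early.
- The gap after treatment 8 concerns scheduled contact only. Visit 8 has its own post-treatment examination, women are encouraged to make contact at any time and can be examined at an unscheduled visit (7.3.6), and complications are followed for at least two years (7.8).
- Section 10.4.4 sets no formal safety endpoint, and testing the long-range risks is not a study objective.

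All of this stands, and it narrows the point. It does not remove it. An inquiry is not an examination. The photographs have no safety reader. Unscheduled visits depend on the woman, and the two-year follow-up starts only once a complication is known. The checks at Visits 2-8 are made on skin that has just been heated, where redness could hide a subtle pigment change (an inference), and they cannot cover later effects of the eighth session or of the full course.

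**Conclusion.** The concern holds as a gap in structured ascertainment. Eight treated-area examinations are scheduled, all immediately after a treatment. None is scheduled at Visit 9, and no contact is scheduled for 70-98 days after the last session. The schedule facts come directly from the text and need no assumption.

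The effect on inference is bounded below and otherwise open. Zero events in 45 women would support an upper limit of 6.4% at best. Any larger figure, including the 7.2% to 12.9% range, rests on an assumed detection rate and should not be presented as a finding about this trial. The elasticity endpoint is unaffected. This is an inexpensive improvement to safety ascertainment that the sponsor should make.

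**What to change.** In 7.3.4, 7.3.5 and the 7.3.7 table, add a treated-area examination at Visit 9, including when that visit is used for early termination. Use the existing none/mild/moderate/severe form with lines for scarring, skin breakdown, hyper- and hypopigmentation and hair loss. Compare the findings with the screening examination and the baseline photographs.

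The cost is a few minutes per woman at a visit already scheduled, some added form lines and a protocol amendment, with no extra visit or staff. The downside is that more minor skin findings will be recorded.

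An AE telephone call about one week after Visit 8 is optional. Under 5.3 "email and phone calls will be employed to remind patients of treatment and follow up appointments", so the site already telephones participants. Those calls are appointment reminders, however, so an AE inquiry would be an added task of up to 45 calls for 45 women. Extra pre-treatment recordings at Visits 2-8 would add up to 7 × 45 = 315 assessments and are not needed to close the gap at Visit 9.
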